1.3. Statistical Hypotheses for Trial Objectives

There is no formal hypothesis for this safety study.

1.4. Sample Size Justification

No formal sample size calculation was performed for the study. All the subjects entering this study (54135419TRD3008) are from 1 of the following esketamine Phase 3 studies *ESKETINTRD3001*, *ESKETINTRD3002*, *ESKETINTRD3003*, *ESKETINTRD3004*, *ESKETINTRD3005*, and *ESKETINTRD3006* (US sites only) and will have met the inclusion/exclusion criteria for entry into those studies. It is unknown how many subjects from the previous Phase 3 studies would participate in this study (54135419TRD3008).

1.5. Randomization and Blinding

This is an open label study. Randomization and blinding procedures will not be applicable for this study. All subjects will be allocated to open-label esketamine treatment.

2. GENERAL ANALYSIS DEFINITIONS

2.1. Analysis Phases

This study has 2 analysis phases:

- A 4-week induction phase;
- A variable duration optimization/maintenance phase.

For France, there is an additional 4-week follow-up phase.

Each analysis phase has its own analysis phase start and end dates.

2.1.1. Study Reference Start and End Dates

For subjects who enter the study at the induction phase, the reference start date for the study is defined as the first dose of intranasal study drug in the induction phase. For subjects who directly enter the optimization/maintenance phase of this study, the reference start date is defined as the first dose of intranasal study drug in the optimization/maintenance phase. The reference end date for subjects who have completed/discontinued from the study is the maximum of the date of last visit and trial completion/discontinuation.

2.1.2. Analysis Phase Start and End Dates

Induction Phase

The start date of the induction phase (referred to as, 'IND start date') is the date of the first dose of intranasal study medication in the induction phase. For subjects who continue to the optimization/maintenance phase, the induction phase end date (referred to as, 'IND end date') is the date of first dose of intranasal study medication taken in the optimization/maintenance phase or the date of the last visit in the induction phase if date of the first dose is missing. For subjects who discontinue in the induction phase, IND end date is the maximum of the date of the last visit in the induction phase or the date of early termination from the induction phase.

The start date/time of the induction phase (referred to as, 'IND start date/time') is the IND start date and the time of the first dose of intranasal study medication in this phase. If no intranasal study medication is administered, the time will be left blank.

The start and end dates for the induction phase are only defined for subjects who enter the study at the induction phase.

Optimization/Maintenance Phase

The start date of the optimization/maintenance phase (referred to as, 'OP/MA start date') is the OP/MA start date of the first dose of intranasal study medication in this phase. For subjects who complete/discontinue from the optimization/maintenance phase, the phase end date (referred to as, 'OP/MA end date') is the maximum of the date of the last visit in the optimization/maintenance phase or the date of completion/withdrawal from the optimization/maintenance phase.

The start date/time of the optimization/maintenance phase (referred to as, 'OP/MA start date/time') is the OP/MA start date and the time of the first dose of intranasal study medication in this phase.

Follow-Up Phase

The start date of the follow-up (post-treatment) phase (referred to as, 'F/U start date') is the day after the end date of the last treatment phase in which the subject participated. For subjects who complete/discontinue from the follow-up phase, the follow-up phase end date (referred to as, 'F/U end date') is the maximum of the last follow-up visit date or end of trial date.

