2.6. Imputation Rules for Missing Adverse Event (AE) Dates

Treatment-emergent adverse events (TEAEs)

- For subjects who enter the study at the induction phase, treatment-emergent AEs are those events with an onset date/time on or after the start of IND phase study medication, and occurred on or before the end of the optimization/maintenance phase. A conservative approach will be used to handle the missing dates for AEs
- For subjects who directly enter the optimization/maintenance phase of this study, treatment-emergent AEs are those events with an onset date/time on or after the start of OP/MA phase study medication, and occurred on or before the end of the optimization/maintenance phase. A conservative approach will be used to handle the missing dates for AEs

Onset Date

AEs for each phase are those events with an onset date/time on or after the start of that particular phase and occurred on or before the end of that phase. The rules for estimating incomplete AE onset dates will be as follows:

Subject Entry into 54135419TRD3008 at the IND Phase:

If the onset date of an adverse event is missing the day only, it will be set to:

- i) First day of the month that the AE occurred, if month/year of the onset of AE is different than the month/year of IND start date
- ii) The day of IND start date, if the month/year of the onset of AE is the same as month/year of the IND start date and month/year of the AE resolution date is different
- iii) The day of IND start date or day of AE resolution date, whichever is earliest, if month/year of the onset of AE and month/year of the IND start date and month/year of the AE resolution date are the same.

If the onset date of an adverse event is missing both day and month, it will be set to the earliest of:

- i) January 1 of the year of onset, as long as this date is after the IND start date
- ii) One day after the IND start date, if this date is the same year that the AE occurred.

A completely missing onset date of an adverse event will be set to the IND start date.

Subject Entry into 54135419TRD3008 at the OP/MA Phase:

If the onset date of an adverse event is missing day only, it will be set to:

- i) First day of the month that the AE occurred, if month/year of the onset of AE is different than the month/year of OP/MA start date
- ii) The day of OP/MA start date, if the month/year of the onset of AE is the same as month/year of the OP/MA start date and month/year of the AE resolution date is different

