- iii) The day of OP/MA start date or day of AE resolution date, whichever is earliest, if month/year of the onset of AE and month/year of the OP/MA start date and month/year of the AE resolution date are the same.

If the onset date of an adverse event is missing both day and month, it will be set to the earliest of:

- i) January 1 of the year of onset, as long as this date is after the OP/MA start date
- ii) One day after the OP/MA start date, if this date is the same year that the AE occurred.

A completely missing onset date of an adverse event will be set to the OP/MA start date.

Resolution Date

The missing day of resolution of an adverse event will be set to the last day of the month of resolution.

If the resolution date of an adverse event is missing both day and month, it will be set to December 31 of the year.

A completely missing resolution date of an adverse event that is not recorded as ongoing will be set to the date of withdrawal or study completion.

Subject Entered into 54135419TRD3008 at the IND Phase:

If the time of onset is missing, it will be imputed as follows:

- i) 00:00 if the date of onset is after IND start date
- ii) The time of intranasal medication start in the IND phase if the date of onset is the same as IND start date

Subject Entered into 54135419TRD3008 at the OP/MA Phase:

If the time of onset is missing, it will be imputed as follows:

- i) 00:00 if the date of onset is after OP/MA start date
- ii) The time of intranasal medication start in the OP/MA phase if the date of onset is the same as OP/MA start date

If a missing time is associated with a partial or missing date, the date will be imputed first prior to imputing the time.

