6.1. Adverse Events

The Medical Dictionary for Regulatory Activities (MedDRA) (version 18.1 or above) will be used to classify AEs by system organ class and preferred term. TEAEs that occurred in each study phase will be summarized by system organ class and preferred term.

The number (%) of subjects with TEAEs, serious TEAEs (SAEs), and TEAEs that led to study drug discontinuation will be summarized by system organ class and preferred term. Data listings will be generated for deaths, other SAEs, and discontinuations due to AEs.

In addition, data listing and summary will be provided for subjects with AEs ongoing at the time of entry into this study.

A TEAE is an event that is new in onset or increased in severity following treatment initiation. An event that starts prior to, and ends after the initiation of study medication will be considered treatment-emergent only if the severity increases after the start of medication.

Treatment-emergent adverse events (TEAEs) are defined as follows for each study phase:

- TEAEs in the induction phase:
 - a. If AE onset time is not missing:
 - i) If subjects continue to OP/MA phase: IND phase start date/time \leq AE onset date and time $<$ IND phase end date
 - ii) If subjects discontinue in the IND phase: IND phase start date/time \leq AE onset date and time \leq IND phase end date

-
- b. If AE onset time is missing:
 - i) If subjects continue to OP/MA phase: IND phase start date/time \leq AE onset date $<$ IND phase end date
 - ii) If subjects discontinue in the IND phase: IND phase start date/time \leq AE onset date \leq IND phase end date
 - TEAEs in the optimization/maintenance phase:
 - a. If AE onset time is not missing: OP/MA phase start date/time \leq AE onset date and time \leq OP/MA phase end date
 - b. If AE onset time is missing: OP/MA phase start date \leq AE onset date \leq OP/MA phase end date
 - For the AEs that have both day and month missing, treatment-emergent flag is assigned based on the rules presented in Section 2.6.

In addition, TEAEs will be summarized by severity and relationship to study medication using the preferred term. For the summaries of TEAEs by severity/relationship to study medication, the observation with the most severe occurrence/closest relationship to study medication will be chosen if there is more than one incident of an AE reported during the analysis phase by the subject. AE duration for transient dizziness/vertigo and anxiety will also be summarized.

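### For subjects who continue from induction, an adverse event timed on the first OP/MA dosing day but before that dose falls in neither phase TEAE table

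*SAP*

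**What the plan says.** Three parts of the SAP decide which phase an adverse event belongs to.

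- **SAP 2.1.2.** For a subject who continues, the IND end date "is the date of first dose of intranasal study medication taken in the optimization/maintenance phase". Start date/times are defined for both phases, but IND has no end time.
- **SAP 6.1.** The IND rule for continuing subjects opens "If subjects continue to OP/MA phase: IND phase start date/time" and requires onset strictly before the IND end date. For subjects who discontinue in IND, the end date is included. The OP/MA rule has two branches. Branch a begins "If AE onset time is not missing: OP/MA phase start date/time" and so starts at the clock time of the first OP/MA dose. Branch b begins "If AE onset time is missing: OP/MA phase start date" and uses the date alone.
- **SAP 2.6.** For IND entrants, an event is treatment-emergent over the whole study if it has "an onset date/time on or after the start of IND phase study medication, and occurred on or before the end of the optimization/maintenance phase". A separate sentence places an event in a phase by "onset date/time on or after the start of that particular phase and occurred on or before the end of that phase". For IND entrants a missing onset time becomes "00:00 if the date of onset is after IND start date". For direct OP/MA entrants it becomes "The time of intranasal medication start in the OP/MA phase if the date of onset is the same as OP/MA start date".

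The protocol's OP/MA Time and Events Schedule (footnote b) expects Visit 1.9 (Day 28) to coincide with Visit 2.1. In the induction schedule, hematology/chemistry, urinalysis and nasal examination fall only on Days 1 and 28, pre-dose when the day is a dosing day.

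**The concern.** Treatment-emergent adverse events are named in the primary safety objective and are tabulated by phase (SAP 6 and 6.1). Every event after the first dose should fall in one phase, and the phase tables should reconcile with the entire-period table. Here the end of IND is a date and the start of OP/MA is a date and time, so the hours between midnight and the first OP/MA dose belong to neither phase.

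Those hours are not an arbitrary slice of the calendar. When Visits 1.9 and 2.1 coincide, they contain the Day 28 pre-dose assessments, and protocol 9.2 requires clinically relevant changes to be recorded as adverse events. Two programmers who follow different sections of the SAP would also build different phase tables from the same data.

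**Working it through.** The plan has no figure of its own to reproduce, so the check applies the rules literally to one illustrative subject. Dates and clock times are assumed: first IND dose 1 March 10:00, first OP/MA dose 28 March 10:00. The IND end date is then 28 March, and the OP/MA start date/time is 28 March 10:00.

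Rules applied:

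- 6.1 IND (continuing): IND start date/time ≤ onset < 28 March.
- 6.1 OP/MA, branch a: 28 March 10:00 ≤ onset ≤ OP/MA end date.
- 6.1 OP/MA, branch b: 28 March ≤ onset date ≤ OP/MA end date.
- 2.6 phase sentence: phase start ≤ onset, on or before the phase end date.
- Shared boundary (the fix): IND if onset < 28 March 10:00, otherwise OP/MA; untimed events of that day go to OP/MA.

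| Onset | 6.1 as written | 2.6 phase sentence | Entire period (2.6) | Shared boundary |
|---|---|---|---|---|
| 27 March 20:00 | IND | IND | yes | IND |
| 28 March 08:00 | neither | IND | yes | IND |
| 28 March 09:00, timed at the pre-dose sample | neither | IND | yes | IND |
| 28 March 11:00 | OP/MA | both | yes | OP/MA |
| 28 March, untimed, branch b applied | OP/MA | IND if 00:00 is imputed | yes | OP/MA |
| 28 March, untimed, 00:00 imputed before 6.1 | neither | IND | yes | OP/MA |

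**Minutes of that day.** With a 10:00 dose, 10 × 60 = 600 minutes are in neither phase under 6.1. Reading the IND end date as the end of that day closes the gap, but then 1440 − 600 = 840 post-dose minutes count in both phases. With the shared boundary, 0 minutes are unassigned and 0 are assigned twice.

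**Share of time.** Day 1 to Day 28 at the same clock time is 27 × 24 = 648 hours. If the dose is at 08:00 to 16:00 (assumed), the gap is 8 to 16 hours: 8/648 = 1.2% and 16/648 = 2.5%. With the ±1 day visit window the denominator is 624 to 672 hours, and the range is 8/672 = 1.2% to 16/624 = 2.6%. This is a share of time, not of events.

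**The case against.** The strongest reply is that the SAP does assign the event. The 2.6 phase sentence includes the end date, so a pre-dose event is IND, and the SAP states no order of precedence. A programmer might also read the IND end date in 6.1 as the date and time of the first OP/MA dose, since 2.1.2 ties the end of IND to that dose. The study is uncontrolled and descriptive, with no hypothesis, so no inference turns on this.

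Part of this stands. The text is loose about dates and date/times, loss from the phase tables is not certain in practice, and the effect is limited. But 6.1 is the section that defines TEAEs phase by phase. The 2.6 sentence does not repair it, because its inclusive end date puts post-dose events of the same day in both phases. Reading the end date as the dose date/time does close the gap, but 2.1.2 gives IND no end time, so that reading has to be written down.

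A reader might infer more than the documents support:

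- *That events disappear from the safety report.* They do not. The 2.6 definition keeps them in the entire-period table.
- *That induction loses its only post-baseline hematology/chemistry, urinalysis and nasal examination.* It does not. SAP Table 1 files the Day 28 results under IND, and SAP 6.2 and 6.5 summarize or list them by phase from the results themselves. Only an adverse event with onset that day is affected.
- *That most laboratory events are exposed because the one scheduled post-baseline sample falls in the gap.* That counts assessments, not events. Under 6.1 as written, the event also needs a recorded clock time before the dose, and the documents do not say how often that is recorded.

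**Conclusion.** The gap is real on the wording of SAP 2.1.2 and 6.1, and 2.6 contradicts it rather than resolving it. It affects the two phase TEAE tables only, for subjects who continue from induction, on one day each, between midnight and the first OP/MA dose. Direct OP/MA entrants are unaffected. If the 2.6 midnight imputation is run before the 6.1 test, untimed events of that day, including those after the dose, also fall in neither phase. The SAP does not state that order.

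The number of events is not given and is probably small. The last induction dose is scheduled for Day 25, so few acute drug effects should start in these hours. Visit 1.9 is expected, not required, to coincide with Visit 2.1; if it falls on an earlier day, its events are IND. The percentages rest on assumed dosing hours. The correction is worth making because the rule misplaces events on a planned visit day and costs little to repair.

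**What to change.** - **SAP 6.1, continuing subjects.** Use one shared boundary. IND: IND start date/time ≤ onset < OP/MA start date/time. OP/MA: OP/MA start date/time ≤ onset ≤ OP/MA end date. Keeping the OP/MA end date as the upper limit leaves the French follow-up events in their own listing.
- **SAP 2.6.** Replace the phase sentence with a reference to 6.1. For IND entrants, set a missing onset time on the OP/MA start date to the time of the first OP/MA dose. This agrees with branch b of 6.1 and with the rule for direct entrants.
- **Table footnote.** State that untimed events on that day are counted in OP/MA by convention, including any untimed event from the Day 28 pre-dose assessments. The convention leaves such an event in OP/MA while the result behind it stays in IND, so it should be visible.
- **Missing first OP/MA dose date.** SAP 2.1.2 then ends IND on the last IND visit. State that this date is inclusive. This is an added rule, because 6.1 now uses a strict inequality for continuing subjects.

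The cost is a few SAP sentences and one footnote. The dose times and onset fields are ones the SAP rules already use, so no new data are needed.

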2.1.3. Study Day and Relative Day

Study day is calculated relative to the reference start date for the study. Relative day is calculated relative to the analysis phase start date of the analysis phase in which the data are captured. A minus (-) sign indicates days prior to the start of study or prior to the start of the analysis phase.

Study day for an event on or after the start of the study is calculated as:

event date - reference start date + 1.

Study day for an event prior to the start of the study is calculated as:

event date - reference start date.

Relative day for an event on or after the analysis phase start date is calculated as:

event date - analysis phase start date + 1.

Relative day for an event prior to the analysis phase start date is calculated as:

event date - analysis phase start date.

There is no study day 0 or relative day 0.

2.2. Baseline and End Point

Baseline is defined for each parameter/assessment.

- Study Baseline: For subjects who enter the study at the induction phase, the last observation prior to or on the start date of induction phase is denoted as 'Baseline'; for subjects who directly enter the study at the optimization/maintenance phase, the last observation prior to or on the start date of optimization/maintenance phase is denoted as 'Baseline'.
- Baseline (OP/MA): The last observation prior to or on the start date of the optimization/maintenance phase is denoted as 'Baseline (OP/MA)'.

Note:

- The 'Study Baseline' value is used to describe the change from baseline in the safety analysis unless otherwise specified.
- For subjects who enter the study at the induction phase, the 'Baseline (IND)' value is used for the efficacy analysis for the induction phase.; for subjects who enter the optimization/maintenance phase, the 'Baseline (OP/MA)' is used for the efficacy analysis for the optimization/maintenance phase.

For each variable measured over time, the 'End Point (IND)' value is defined as the last postbaseline assessment value during the induction phase for subjects who enter the study at the induction phase.

The ‘End Point (OP/MA)’ value is defined as the last postbaseline assessment value during the optimization/maintenance phase.

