The mean (SD) peak systolic blood pressure (SBP) after the first administration in each dose group was:

- Placebo: 124.2 (11.51) mm Hg (mean [SD] increase of 5.4 [7.84] mm Hg)
- 28 mg: 131.8 (15.49) mm Hg (mean [SD] increase of 10.4 [10.44] mm Hg)
- 56 mg: 130.4 (18.64) mm Hg (mean [SD] increase of 11.2 [15.01] mm Hg)
- 84 mg: 146.1 (19.9) mm Hg (mean [SD] increase of 17.1 [15.5] mm Hg)

Mean (SD) peak diastolic blood pressure (DBP) after the first administration in each dose group was:

- Placebo: 81.2 (8.36) mm Hg (mean [SD] increase of 3.8 [7.99] mm Hg)
- 28 mg: 85.7 (9.16) mm Hg (mean [SD] increase of 6.5 [7.00] mm Hg)
- 56 mg: 86.5 (11.34) mm Hg (mean [SD] increase of 7.2 [9.67] mm Hg)
- 84 mg: 87.8 (10.62) mm Hg (mean [SD] increase of 8.1 [9.12] mm Hg)

The blood pressure increase typically resolved within 2 hours. Unlike dissociative symptoms, the blood pressure changes observed do not appear to attenuate over time with multiple doses. Transient increases in heart rate were also observed in parallel with blood pressure change. There was no clinically meaningful change in blood oxygen level.

Adverse Events Associated with Chronic Use of Ketamine

There are no controlled studies of long-term use with esketamine/ketamine in patients with MDD. Much of the literature on chronic use of ketamine comes from data gathered from street/illegal use of the drug, rather than systematically conducted clinical studies. Data therefore should be interpreted with caution, as in many cases, no baseline pre-drug data are available and drug exposure is poorly documented.

In a 1-year longitudinal study, 150 subjects were divided into 5 groups of 30 subjects each: frequent ketamine users (more than 4 times per week), infrequent ketamine users (at least once a month), abstinent users (abstinent for at least 1 month), polydrug controls, and non-users of illicit

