		22 + i*14	Week (4 + i*2) (OP/MA)	16 + i*14 to 29 + i*14	22 + i*14
OP/MA final visit	End Point (OP/MA)	2 to end of OP/MA			
Patient Health Questionnaire – 9 item (PHQ-9), EuroQol Group; 5 dimension; 5 level (EQ-5D-5L), Quality of Life in Depression Scale (QLDS)	IND	1	Baseline	≤ 1	1
		15	Day 15 (IND)	2 - 21	15
		28	Day 28 (IND)	22 to end of IND	28
	IND final visit	End Point (IND)	2 to end of IND		
	OP/MA i=1,2,3,...	1	Baseline (OP/MA)	≤ 1	1
		15	Week 3 (OP/MA)	2 - 32	15
		50	Week 8 (OP/MA)	33 - 64	50
		50 + i*28	Week (8 + i*4) (OP/MA)	37 + i*28 to 64 + i*28	50 + i*28
OP/MA final visit	End Point (OP/MA)	2 to end of OP/MA			
Sheehan Disability Scale (SDS)	IND	1	Baseline	≤ 1	1
		28	Day 28 (IND)	2 to end of IND	28
		IND final visit	End Point (IND)	2 to end of IND	
	OP/MA i=1,2,3,...	1	Baseline (OP/MA)	≤ 1	1
		15	Week 3 (OP/MA)	2 - 32	15
		50	Week 8 (OP/MA)	33 - 64	50
		50 + i*28	Week (8 + i*4) (OP/MA)	37 + i*28 to 64 + i*28	50 + i*28
	OP/MA final visit	End Point (OP/MA)	2 to end of OP/MA		
Treatment Satisfaction Questionnaire for Medication (TSQM-9)	IND	1	Baseline	≤ 1	1
		28	Day 28 (IND)	2 to end of IND	28
		IND final visit	End Point (IND)	2 to end of IND	
	OP/MA i=1,2,3,...	1	Baseline (OP/MA)	≤ 1	1
		50	Week 8 (OP/MA)	2 - 64	50
		50 + i*28	Week (8 + i*4) (OP/MA)	37 + i*28 to 64 + i*28	50 + i*28
OP/MA final visit	End Point (OP/MA)	2 to end of OP/MA			
	IND	28	Day 28 (IND)	1 to end of IND	28

Table 1: Analysis Visits

Parameter	Analysis Phase	Scheduled Day ^a	Time Interval (label on output)	Time Interval ^a (Day)	Target Time Point ^a (Day)
Patient Stated-choice Preference	OP/MA	22	Week 4 (OP/MA)	1 to end of OP/MA	22
Nasal exam	IND	1	Baseline	≤ 1	1
		28	Day 28 (IND)	2 to end of IND	28
		IND final visit	End Point (IND)	2 to end of IND	
Vital Signs: Temperature (TEMP) (IND [predose], OP/MA [predose]), Blood Pressure (BP) ^b , Hear Rate (HR), Respiratory (RESP) (IND [predose, 40M, 1H, 1H30M], OP/MA [predose, 40M, 1H])	IND	1	Baseline	≤ 1 / predose	1
			Day 1 (IND): 40M		
			Day 1 (IND): 1H		
			Day 1 (IND): 1H30M		
		4	Day 4 (IND): Predose	2 - 6	4
			Day 4 (IND): 40M		
			Day 4 (IND): 1H		
			Day 4 (IND): 1H30M		
		8	Day 8 (IND): Predose	7 - 9	8
			Day 8 (IND): 40M		
			Day 8 (IND): 1H		
			Day 8 (IND): 1H30M		
		11	Day 11 (IND): Predose	10 - 13	11
			Day 11 (IND): 40M		
			Day 11 (IND): 1H		
			Day 11 (IND): 1H30M		
		15	Day 15 (IND): Predose	14 - 16	15
			Day 15 (IND): 40M		
			Day 15 (IND): 1H		
			Day 15 (IND): 1H30M		
		18	Day 18 (IND): Predose	17 - 20	18

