			Day 18 (IND): 40M		
			Day 18 (IND): 1H		
			Day 18 (IND): 1H30M		
		22	Day 22 (IND): Predose	21 - 23	22
			Day 22 (IND): 40M		
			Day 22 (IND): 1H		
			Day 22 (IND): 1H30M		
25	Day 25 (IND): Predose	24 to end of IND	25		
	Day 25 (IND): 40M				
	Day 25 (IND): 1H				
	Day 25 (IND): 1H30M				
IND final visit	IND final visit	End Point (IND)	Day 1 (IND): 40M to end of IND		

Table 1: Analysis Visits

Parameter	Analysis Phase	Scheduled Day ^a	Time Interval (label on output)	Time Interval ^a (Day)	Target Time Point ^a (Day)
	OP/MA i=1,2,3,...	1	Baseline (OP/MA)	≤ 1	1
			Week 1 (OP/MA): 40M		
			Week 1 (OP/MA): 1H		
		8	Week 2 (OP/MA): Predose	2 - 11	8
			Week 2 (OP/MA): 40M		
			Week 2 (OP/MA): 1H		
		15	Week 3 (OP/MA): Predose	12 - 18	15
			Week 3 (OP/MA): 40M		
			Week 3 (OP/MA): 1H		
		22	Week 4 (OP/MA): Predose	19 - 25	22
			Week 4 (OP/MA): 40M		
			Week 4 (OP/MA): 1H		
		22 + i*7	Week (4 + i*1) (OP/MA): Predose	19 + i*7 to 25 + i*7	22 + i*7
Week (4 + i*1) (OP/MA): 40M					
Week (4 + i*1) (OP/MA): 1H					
OP/MA final visit	End Point (OP/MA)	Week 1: 40M to end of OP/MA			
Weight and body mass index (BMI), Hematology and Chemistry, Urinalysis	IND	1	Baseline	≤ 1	1
		28	Day 28 (IND)	2 to end of IND	28
		IND final visit	End Point (IND)	2 to end of IND	
	OP/MA i=1,2,3,...	1	Baseline (OP/MA)	≤ 1	1
		106	Week 16 (OP/MA)	2 - 148	106
		106 + i*84	Week (16 + i*12) (OP/MA)	65 + i*84 to 148 + i*84	106 + i*84
		OP/MA final visit	End Point (OP/MA)	2 to end of OP/MA	
Electrocardiogram (ECG)	IND	1	Baseline	≤ 1 / predose	1
			Day 1 (IND): 1H		
		15	Day 15 (IND): 1H	2 - 20	15
		25	Day 25 (IND): 1H	21 to end of IND	25
	IND final visit	End Point (IND)	Day 1 (IND): 1H to end of IND		
	OP/MA i=1,2,3,...	1	Baseline (OP/MA)	≤ 1	1
			Week 1 (OP/MA): 1H		
		50	Week 8 (OP/MA): 1H	2 - 64	50
50 + i*28		Week (8 + i*4) (OP/MA): 1H	37 + i*28 to 64 + i*28	50 + i*28	

Table 1: Analysis Visits

Parameter	Analysis Phase	Scheduled Day ^a	Time Interval (label on output)	Time Interval ^a (Day)	Target Time Point ^a (Day)	
		OP/MA final visit	End Point (OP/MA)	Week 1: 1H to end of OP/MA		
Columbia-Suicide Severity Rating Scale(C-SSRS)	IND	1	Baseline	≤ 1	1	
		4	Day 4 (IND)	2 - 6	4	
		8	Day 8 (IND)	7 - 9	8	
		11	Day 11 (IND)	10 - 13	11	
		15	Day 15 (IND)	14 - 16	15	
		18	Day 18 (IND)	17 - 20	18	
		22	Day 22 (IND)	21 - 23	22	
		25	Day 25 (IND)	24 - 26	25	
		28	Day 28 (IND)	27 to end of IND	28	
	IND final visit	End Point (IND)	2 to end of IND			
	OP/MA i=1,2,3,...	1	Baseline (OP/MA)	≤ 1	1	

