6.3. Vital Signs, Weight, and BMI

Descriptive statistics for values and changes from Baseline values (described in Section 2.2) at each scheduled time-point during the induction and optimization/maintenance phases will be presented for temperature, systolic blood pressure, diastolic blood pressure, pulse rate, respiratory rate, oxygen saturation, weight, and BMI. Baseline will be used for change summaries and to determine abnormal values during all treatment phases (IND and OP/MA). Graphical presentations will be provided.

In addition, descriptive statistics of pulse rate and blood pressure (systolic and diastolic) values and changes and percent changes from predose will be provided for each intranasal dosing day.

The proportion of subjects who have a treatment-emergent abnormality, as defined in Table 4 below, during each treatment phase will be presented. A listing of subjects meeting any of the following criteria during each treatment phase will also be provided.

Table 4: Treatment-Emergent Abnormality Categories for Vital Signs

Vital Parameter	Post-baseline value outside of normal limit if:	
	Abnormally low	Abnormally high
Pulse (bpm)	A decrease from Baseline of ≥ 15 to a value ≤ 50	An increase from Baseline of ≥ 15 to a value ≥ 100
Systolic BP (mmHg)	A decrease from Baseline of ≥ 20 to a value ≤ 90	An increase from Baseline of ≥ 20 to a value ≥ 180
Diastolic BP (mmHg)	A decrease from Baseline of ≥ 15 to a value ≤ 50	An increase from Baseline of ≥ 15 to a value ≥ 105

BP = blood pressure; Baseline is defined in Section 2.2.

The proportion of subjects who experienced treatment-emergent acute hypertension (systolic BP ≥ 180 or diastolic BP ≥ 110) at any time during each treatment phase will be summarized by hypertension status.

Mean (+/-SE) values for systolic BP, diastolic BP and heart rate will be summarized by hypertension status and presented graphically for each treatment phase. In addition, for subjects with hypertension who receive antihypertensive medication, the same tables and graphs will be summarized by medication type (beta-blockers, all other agents).

A listing of subjects with oxygen saturation less than 93% will be provided.

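### SAP 2.2 fixes baseline by calendar date, not first-dose time: uncorrected for pulse oximetry, and in conflict with SAP Table 1 for optimization/maintenance blood pressure, pulse and respiratory rate

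*SAP*

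**What the plan says.** **The rule.** For direct entrants to OP/MA, SAP 2.2 states that "the last observation prior to or on the start date of optimization/maintenance phase is denoted as" baseline. Induction entrants and Baseline (OP/MA) have parallel date-based wording. The same section adds that "The 'Study Baseline' value is used to describe the change from baseline in the safety analysis unless otherwise specified".

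**The unused clock time.** SAP 2.1.2 defines an OP/MA start date/time, which "is the OP/MA start date and the time of the first dose of intranasal study medication in this phase". SAP 6.1 uses start date/times to classify adverse events. SAP 2.2 does not use them.

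**Table 1, vital signs.** The OP/MA schedule is "OP/MA [predose, 40M, 1H". The induction baseline window carries a predose label; the OP/MA baseline window reads only Day 1 or earlier. Day 1 postdose readings have their own rows, such as "Week 1 (OP/MA): 40M", and the OP/MA End Point window is "Week 1: 40M to end of OP/MA".

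**Table 1, pulse oximetry.** The parameter heading lists predose and postdose times in both phases. The rows themselves have no predose label and no separate Day 1 postdose entries, and End Point starts on Day 2. OP/MA has a Week 1 row but none called baseline.

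**Outputs, SAP 6.3.** Changes from baseline are summarized for all vital signs and oxygen saturation. Table 4, whose footnote refers to SAP 2.2, flags high systolic pressure as "An increase from Baseline of ≥ 20 to a value ≥ 180", high diastolic pressure as a rise of at least 15 to at least 105, and high pulse as a rise of at least 15 to at least 100. Separate outputs are a change-from-predose summary for pulse and blood pressure, an acute-hypertension count on absolute limits (180 systolic or 110 diastolic), and a listing of saturation below 93%.

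**The concern.** On a dosing day these parameters are measured before the dose and again up to an hour after it. By date alone, the last observation on Day 1 is the 1-hour reading. A programmer who follows SAP 2.2 to the letter would therefore measure the drug's acute effect against a value that already contains it.

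Postdose effects on heart rate, blood pressure, respiratory rate and oxygen saturation are named in the primary objective. With a postdose baseline, mean postdose changes shrink toward zero, later predose values look like falls, and the rise half of the Table 4 high criteria becomes harder to meet, while the fall half of its low criteria becomes easier.

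**Working it through.** **1. Which parameters does Table 1 rescue?**

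| Parameter | What Table 1 adds to SAP 2.2 | Result |
|---|---|---|
| Vital signs, induction | Predose label on the baseline window | Resolved |
| Blood pressure, pulse, respiratory rate, OP/MA | No label, but separate 40-minute and 1-hour rows and End Point from the Week 1 40-minute reading | Table implies predose; text does not |
| Pulse oximetry, both phases | No label, no Day 1 postdose rows, End Point from Day 2 | Not resolved |
| ECG, OP/MA | No label; a Week 1 1-hour row | Unclear: protocol footnote n (OP/MA Time and Events Schedule) appears to schedule only a predose ECG at Visit 2.1 |

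**2. Which outputs depend on baseline?** The change-from-baseline summaries and Table 4 do. For respiratory rate and saturation, change from baseline is the only change summary, because the change-from-predose display covers only pulse and blood pressure.

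**3. Table 4 with a predose baseline.** Protocol 4.2 caps predose pressure at first dose at 140/90, or 150/90 from age 65.

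- Systolic 180 is then a rise of at least 180 − 140 = 40, or 180 − 150 = 30; the rule needs 20.
- Diastolic 105 is a rise of at least 105 − 90 = 15; the rule needs 15.

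The rise condition is always met, so no high blood pressure reading is missed.

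**4. Table 4 with a 1-hour baseline.** A later systolic of 180 is missed if baseline exceeded 180 − 20 = 160; a later diastolic of 105 is missed if it exceeded 105 − 15 = 90. Example: predose 135, Day 1 1-hour 165, later reading 184. The rise is 49 from predose (flagged) but 19 from the 1-hour value (not flagged). The acute-hypertension count includes it either way.

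**5. How often.** The plan gives no figure to reproduce. The illustration uses the Phase 2 peaks in Protocol 1.1.2.3: "84 mg: 146.1 (19.9) mm Hg (mean [SD] increase of 17.1 [15.5] mm Hg". If the rise is independent of the predose value, predose systolic has mean 146.1 − 17.1 = 129 and SD √(19.9² − 15.5²) ≈ 12.5. I truncated it at 140 and simulated two sessions with normal rises. The table gives the share of second-session readings of 180 or more whose increase over the first-session postdose value is below 20. All three varied quantities are assumptions.

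| Predose value across sessions | 1-hour rise as share of peak | Missed, for between-session correlation of the rise 0.3 / 0.5 / 0.7 |
|---|---|---|
| Identical | 100% | 38% / 57% / 80% |
| Correlation 0.5 | 100% | 26% / 41% / 60% |
| Identical | 60% | 6% / 11% / 18% |
| Correlation 0.5 | 60% | 3% / 6% / 10% |

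Readings of 180 or more are about 1.4% to 1.6% of second-session values. Capping predose values at 140 instead of truncating raises the first row to 43% / 61% / 82%.

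**6. Diastolic 105 to 109.** This band lies below the absolute limit of 110, so Table 4 is the only threshold count that reaches it. The 84 mg peak is 87.8 (SD 10.62) and the rise 8.1 (SD 9.12), so predose has mean 79.7 and SD √(10.62² − 9.12²) ≈ 5.4, truncated at 90. About 3% of second-session readings fall in the band. The share missed is about 68% / 82% / 94% under the first row's assumptions and 32% / 42% / 54% under the last row's.

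**The case against.** The strongest reply is that Table 1 already makes the OP/MA vital-sign baseline predose. Weeks 2 to 4 each list predose, 40 minutes and 1 hour; Week 1 lists baseline, 40 minutes and 1 hour, so baseline fills the predose slot. End Point is defined as the last postbaseline value and may start at the Day 1 40-minute reading, which classes that reading as postbaseline. A 1-hour baseline would also make every direct entrant's Week 1 1-hour change exactly zero. For blood pressure, pulse and respiratory rate this is persuasive as to intent. It does not remove the conflict: Table 4 cites SAP 2.2, and nothing says which governs. It does not reach pulse oximetry at all.

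A reader might infer that a postdose value does become baseline for direct entrants and that treatment-emergent hypertension is thereby hidden. The documents support neither. The first is unsettled for the reasons just given. The second is too broad: the acute-hypertension count has no baseline term and the same systolic limit as Table 4, so every systolic reading of 180 or more is still counted, and pulse and blood pressure are also compared with predose on each dosing day.

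The magnitude is also open to challenge. The Phase 2 values are peaks, whereas the literal baseline would be the 1-hour value, and several direct-entry groups start below 84 mg. The upper figures need identical predose pressure at both sessions and a full peak rise at 1 hour. That criticism stands, and it is why a range is given.

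**Conclusion.** The date-only rule in SAP 2.2 is wrong as written, with minor severity. For pulse oximetry it is uncorrected in both phases, and saturation has no change-from-predose summary to fall back on. For OP/MA blood pressure, pulse and respiratory rate it is a conflict between text and table, with Table 1 pointing to a predose baseline. The OP/MA ECG row lacks the label too, but whether a Day 1 postdose ECG exists is unclear.

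What is at risk is the change-from-Study-Baseline summaries and the Table 4 criteria, with least backup for respiratory rate and saturation changes, high pulse, and diastolic readings of 105 to 109. The loss applies only if the text is programmed literally. The share of systolic readings of 180 or more that Table 4 would then miss runs from about 3% to about 80%, driven by assumed correlations and by how much of the peak rise remains at 1 hour. No such reading is lost from the acute-hypertension count.

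**What to change.** In SAP 2.2, define Study Baseline and Baseline (OP/MA) as the last non-missing observation before the date and time of the first intranasal dose of the study or phase, using the start date/times in SAP 2.1.2. In Table 1, write ≤ 1 / predose in the OP/MA vital-sign baseline row and the Day 1 pulse-oximetry rows of both phases. Add the same label to the OP/MA ECG baseline, and reconcile the Week 1 1-hour ECG entry with protocol footnote n.

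The cost is a few lines of SAP text and one derivation rule. Protocol 9.1.1 already requires actual assessment dates and times to be recorded, so no new data are needed.
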